2.4.4.1.6 Subgroup analyses

To assess the homogeneity of the treatment effect across various subgroups, treatment-bysubgroup factor, time point-by-subgroup factor and treatment-by time point-by subgroup factor interaction terms and a subgroup factor term will be added in the two primary MMRM models (except for the subgroup "Body weight").

LS means difference at Week 24 will be provided, as well as the corresponding SE and 97.5% CIs, within each subgroup for each alirocumab dosing regimen group versus its contemporaneously randomized placebo dosing regimen group (ie, of the same dosing regimen cohort):

- alirocumab Q2W versus placebo Q2W,
- alirocumab Q4W versus placebo Q4W,

The significance level of the treatment-by-subgroup factor interaction term for each alirocumab dosing regimen group versus its contemporaneously randomized placebo group (ie, of the same dosing regimen cohort) at Week 24 will be also provided for each factor group for descriptive purpose. Forest plots will be provided. In order to handle unbalances between randomization stratification factors levels, population weights will be used as for the primary analysis model.

Only subgroups for which we anticipate having enough patients in each level are evaluated.

Subgroups of interest are:

- Body Weight stratum as par IVRS/IWRS ($<50 \text{ kg}, \ge 50 \text{ kg}$),
- Gender (Female, Male),
- Age (<12 years, \geq 12 years),
- Baseline LDL-C: < 160 mg/dl; $\geq 160 \text{ mg/dL}$.

2.4.4.2 Analyses of secondary efficacy endpoints

2.4.4.2.1 Continuous endpoints anticipated to have a normal distribution

Continuous secondary efficacy endpoints defined in Section 2.1.3.2 analyzed with the ITT estimand and anticipated to have a normal distribution [ie, lipids other than TG and Lp(a)] will be analyzed using the same MMRM models as for the primary endpoint with the corresponding baseline and post-baseline values in the ITT population.

Continuous secondary efficacy endpoints analyzed with the on-treatment estimand and anticipated to have a normal distribution will be analyzed using the same MMRM models but only including on-treatment values in the mITT population.

- For the Q2W dosing regimen cohort, the treatment period is defined as the time period from the first double-blind IMP injection up to the day of last double-blind injection +21 days.
- For the Q4W dosing regimen cohort, the treatment period is defined as the time period from the first double-blind IMP injection up to the day of last double-blind injection +35 days for patients who stopped IMP before the switch to Q2W regimen (actual or sham), +21 days otherwise.

In addition, key continuous secondary efficacy endpoints anticipated to have a normal distribution will be analyzed using the same ITT estimand and Pattern Mixture Model for missing data as described for the primary efficacy endpoint in Section 2.4.4.1.4.

2.4.4.2.2 Continuous endpoints anticipated to have a non-normal distribution

Continuous secondary efficacy endpoints defined in Section 2.1.3.2 analyzed with the ITT estimand and anticipated to have a non-normal distribution (ie, TG and Lp(a)), will be analyzed using multiple imputation approach for handling of missing values in the ITT population. The percent change from baseline at time point of interest will be derived from observed and imputed lipid values at this time point.

For the Q2W dosing regimen cohort, multiple imputation will be followed by robust regression model (9) with endpoint of interest as response variable using M-estimation (using SAS ROBUSTREG procedure) with treatment group (alirocumab, placebo), randomization strata (previous participation [yes or no] to DFI14223 study, baseline body weight [<50 or \geq 50 kg]) and corresponding baseline value(s) as effects to compare treatment effects. Combined means

estimates for each treatment group will be provided. The differences of these estimates with their corresponding SEs, 97.5% CIs and p-value will be provided through the SAS MIANALYZE procedure for the comparison of the alirocumab group versus the placebo group.

For the Q4W dosing regimen cohort, the same strategy will be conducted, using a robust regression model with endpoint of interest as response variable using M-estimation with treatment group (alirocumab, placebo) and randomization strata (baseline body weight [$<50 \text{ or } \ge 50 \text{ kg}$]) as main effects and corresponding baseline value as covariate.

For both dosing regimen cohorts, continuous secondary efficacy endpoints analyzed with the ontreatment estimand and anticipated to have a non-normal distribution will be analyzed using the same imputation and analysis models but only including on-treatment values (see Section 2.4.4.2.1) in these models in the mITT population.

Multiple imputation model

Since in general the missing pattern is anticipated to be not monotone, a two-step approach will be used:

- Step 1: The MCMC method will be used in conjunction with the IMPUTE=MONOTONE option to create an imputed data set with a monotone missing pattern;
- Step 2: Using the monotone data set from step 1, missing data will be imputed using the regression method.

The imputation model for step 1 will include the treatment group and the values of the analyzed parameter at baseline and time-points up to Week 24.

The imputation model for step 2 will include the same variables as in step 1 with the following additional variables:

- the randomization strata;
- age and gender (age included as continuous variables).

Data will be log-transformed before imputation process and then back-transformed to create the imputed data sets using the TRANSFORM statement of SAS MI procedure.

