11.4.2.2 Analyses of secondary efficacy endpoints

Multiple types of measurements are planned to be analyzed (see Section 9.2) during differing time points in the trial, specifically continuous measurements expected to have a normal distribution (example: percent change in LDL-C), continuous measurements expected to have a non-normal distribution (example: TG), and binary measurements (example: proportion of patients achieving a LDL-C < 130 mg/dL).

Continuous endpoints anticipated to have a normal distribution

Continuous secondary efficacy endpoints analyzed with the ITT estimand and anticipated to have a normal distribution (ie, lipids other than TG and Lp(a)) will be analyzed within each dosing regimen cohort, using the same MMRM models as for the primary endpoint with the corresponding baseline and post-baseline values.

Continuous secondary efficacy endpoints analyzed with the on-treatment estimand and anticipated to have a normal distribution will be analyzed using the same MMRM models within each dosing regimen cohort, but only including on-treatment values. The treatment period is defined as:

- For the Q2W dosing regimen cohort, the time period from the first double-blind IMP injection up to the day of last double-blind IMP injection +21 days.
- For the Q4W dosing regimen cohort, the time period from the first double-blind IMP injection up to the day of last double-blind IMP injection +35 days for patients who stopped definitively the IMP before the switch to Q2W regimen at Week 12 (actual or sham), +21 days otherwise.

Continuous endpoints anticipated to have a non-normal distribution

Continuous secondary efficacy endpoints analyzed with the ITT estimand and anticipated to have a non-normal distribution (ie, TG and Lp(a)), will be analyzed using a robust regression model (ie, ROBUSTREG SAS procedure with M-estimation option).

For the Q2W dosing regimen cohort, the model will include treatment group (alirocumab, placebo) and randomization strata (previous participation [yes or no] to Phase 2 DFI14223 study, baseline body weight [<50 or ≥ 50 kg]) as main effects and corresponding baseline value as covariate.

For the Q4W dosing regimen cohort, the model will include treatment group and randomization strata (baseline body weight [$<50 \text{ or } \ge 50 \text{ kg}$]) as main effects and corresponding baseline value as covariate.

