1.6 STATISTICAL MODIFICATIONS MADE IN THE STATISTICAL ANALYSIS PLAN

Changes already incorporated in a protocol amendment are listed in Table 2. The statistical analysis plan history table below gives the timing, rationale, and key details for major changes to the statistical analysis features in this amended version of the statistical analysis plan (version 2) compared to the initial version (version 1) of 8 January 2021.

SAP version number	Date approved	Rationale	Description of statistical changes
2	This version	Per protocol, safety assessments (laboratory data, vital signs etc) at Week 24 are measured on the same day as the administration of first open- label injection (just before)	For patients proceeding into the open-label period, the double-blind TEAE period is truncated at the first open-label injection and not the day before (Section 2.1.4)
2	This version	As per regulatory agency's feedback	Unequal variances by treatment group will be implemented for ANCOVA analyses (Section 2.4.4.1.4, Section 2.4.4.4 and Section 2.4.5.7). Consistently, a correlation matrix by treatment group to model within- patients error will be used for the MMRM models (Section 2.4.4.1.1)
2	This version	As per regulatory agency's feedback	In the pattern mixture model (Section 2.4.4.1.4), post-treatment missing values for patients who discontinued the treatment due to the COVID- 19 pandemic will be imputed under missing at random assumption, ie. based on on-treatment values in the same treatment group
2	This version	Simplification	Removal of a sensitivity analysis in Section 2.4.4.1.5 as a similar analysis is already included in Section 2.4.4.1.4
2	This version	As per regulatory agency's feedback	Pattern Mixture Model for key secondary continuous efficacy endpoints normally distributed will be implemented (Section 2.4.4.2.1)
2	This version	As per regulatory agency's feedback	For binary efficacy endpoints, in the situation of data dependent case, post-treatment missing values will be considered as failure (except for patients who discontinue due to the COVID-19 pandemic) (Section 2.4.4.2.3)

Table 3 - Statistical analysis plan statistical changes

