2.1.3.2 Secondary efficacy endpoint(s)

2.1.3.2.1 Key secondary efficacy endpoints

The key secondary efficacy endpoints are:

- Percent change in LDL-C from baseline to Week 12 (ITT estimand).
- Percent change in Apo B from baseline to Week 24 (ITT estimand).
- Percent change in non-HDL-C from baseline to Week 24 (ITT estimand).
- Percent change in Total-C from baseline to Week 24 (ITT estimand).
- Percent change in Apo B from baseline to Week 12 (ITT estimand).
- Percent change in non-HDL-C from baseline to Week 12 (ITT estimand).
- Percent change in Total-C from baseline to Week 12 (ITT estimand).
- Proportion of patients achieving a LDL-C level lower than 130 mg/dL (3.37 mmol/L) at Week 24 (ITT estimand).
- Proportion of patients achieving a LDL-C level lower than 130 mg/dL (3.37 mmol/L) at Week 12 (ITT estimand).

- Proportion of patients achieving a LDL-C level lower than 110 mg/dL (2.84 mmol/L) at Week 24 (ITT estimand).
- Proportion of patients achieving a LDL-C level lower than 110 mg/dL (2.84 mmol/L) at Week 12 (ITT estimand).
- Percent change in Lp (a) from baseline to Week 24 (ITT estimand).
- Percent change in Lp (a) from baseline to Week 12 (ITT estimand).
- Percent change in HDL-C from baseline to Week 24 (ITT estimand).
- Percent change in fasting TG from baseline to Week 24 (ITT estimand).
- Percent change in Apo A-1 from baseline to Week 24 (ITT estimand).
- Percent change in HDL-C from baseline to Week 12 (ITT estimand).
- Percent change in fasting TG from baseline to Week 12 (ITT estimand).
- Percent change in Apo A-1 from baseline to Week 12 (ITT estimand).

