2.4.4.3 Multiplicity issues

The Bonferroni adjustment will be applied to handle multiplicity for the comparison of each alirocumab dosing regimen group versus its contemporaneously randomized placebo group (ie, alirocumab Q2W versus placebo Q2W; alirocumab Q4W versus placebo Q4W) for the primary efficacy endpoint (two-sided 0.025 alpha level will apply for each comparison).

In order to handle multiple key secondary endpoints, the overall type-I error will be controlled by the use of a sequential inferential approach applied independently within each dosing regimen cohort (Q2W and Q4W). Statistical significance of the primary parameter at the two-sided 0.025 alpha level is required before drawing inferential conclusions for that dosing regimen cohort about first key secondary parameter (refer to order of list in Section 2.1.3.2.1. Inferential conclusions about successive key secondary parameters for a given dosing regimen cohort require statistical significance of the prior one in that dosing regimen cohort.

The Bonferroni adjustment and this fixed hierarchical approach will ensure a strong control of the overall type-I error rate at the two-sided 0.05 level.

No further adjustments will be made for other secondary endpoints for which p-values will be provided for descriptive purpose only (no claim).

In addition, no further multiplicity adjustment is needed for multiple analyses (ie, first step and second step analyses, if applicable, see Section 3). All primary and key secondary efficacy endpoints will be fully evaluable at the time of the first step analysis. Analyses of lipid parameters beyond Week 24 will be descriptive.

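### The Lp(a) and TG key secondary tests keep a single-scale M-estimation standard error under 2:1 allocation, so they are mis-sized if the two arms differ in spread

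*SAP*

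**What the plan says.** SAP 2.1.3.2.1 lists 19 key secondary endpoints in testing order. Lp(a) is 12th and 13th, starting with "Percent change in Lp (a) from baseline to Week 24 (ITT estimand"); fasting TG is 15th and 18th, ending with "Percent change in fasting TG from baseline to Week 12 (ITT estimand"). SAP 2.4.4.3 tests them by "a sequential inferential approach applied independently within each dosing regimen cohort", where a "two-sided 0.025 alpha level will apply for each comparison", and states that the scheme "will ensure a strong control of the overall type-I error rate at the two-sided 0.05 level".

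The analysis method is in SAP 2.4.4.2.2: "multiple imputation will be followed by robust regression model (9) with endpoint of interest as response variable using M-estimation (using SAS ROBUSTREG procedure"). The covariates are treatment, randomization strata and baseline. Protocol 11.4.2.2 has the same method: such endpoints "will be analyzed using a robust regression model (ie, ROBUSTREG SAS procedure with M-estimation option"). Neither text names a covariance option, an arm-specific scale or a robust standard error.

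Elsewhere, SAP 1.6 (Table 3) records a version 2 change made after regulatory feedback: "Unequal variances by treatment group will be implemented for ANCOVA analyses". It names sections 2.4.4.1.4, 2.4.4.4 and 2.4.5.7, and a matching change gives the MMRM in 2.4.4.1.1 a covariance matrix for each arm. Both changes have a fallback if the model does not converge. Section 2.4.4.2.2 is not on the list.

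**The concern.** M-estimation protects against outlying values. It does not protect against one arm being more variable than the other. As usually implemented, it estimates one residual scale, and its asymptotic covariance treats the errors as identically distributed. With twice as many patients on alirocumab, that arm largely sets the scale. If placebo is more variable, its legitimate values are down-weighted as outliers and the standard error is too small. If alirocumab is more variable, the standard error is too large.

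Two things are at stake. One is the level of four alpha-controlled tests in each cohort, eight in the trial. The other is the coverage of their 97.5% CIs, which suffers even when a treatment effect exists. An oversized standard error at Lp(a) can also stop the sequence before HDL-C and Apo A-1 are reached.

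Nothing planned would reveal the problem. The residual checks (SAP 2.4.4.1.2) concern the primary MMRM, and the added pattern mixture analyses (2.4.4.2.1) cover only endpoints treated as normal.

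**Working it through.** **Inputs from the documents.** Two-sided alpha is 0.025 per cohort (SAP 2.4.4.3). Each cohort has 50 alirocumab and 25 placebo patients (SAP 1.3). The only SD given is 25%, for LDL-C.

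**The plan's own figure.** The plan states no operating characteristic for Lp(a) or TG. Its LDL-C power uses the same alpha and allocation, for 30 vs 15. SE = 25 × √(1/30 + 1/15) = 7.91, noncentrality = 30/7.91 = 3.79, critical t on 43 df = 2.32, power = 92.5%. This reproduces the stated 92%.

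**Assumptions.** The placebo/alirocumab SD ratio r is unknown and is shown as a range. The single MAD scale and the H1 covariance are taken as the software's behaviour and default; the SAP does not say so.

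**Step 1: closed form for a pooled-variance comparison, before any down-weighting.** Set the alirocumab SD to 1.
- Variance used: (2 + r²)/3 × (1/50 + 1/25) = (2 + r²)/3 × 0.06.
- True variance: 1/50 + r²/25 = 0.02 + 0.04r².
- Actual level: 2 × [1 − Φ(2.2414 × √(used/true))].

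| r | used | true | √(used/true) | level |
|---|---|---|---|---|
| 0.5 | 0.0450 | 0.0300 | 1.225 | 0.006 |
| 0.67 | 0.0489 | 0.0378 | 1.138 | 0.011 |
| 1 | 0.0600 | 0.0600 | 1.000 | 0.025 |
| 1.25 | 0.0713 | 0.0825 | 0.929 | 0.037 |
| 1.5 | 0.0850 | 0.1100 | 0.879 | 0.049 |
| 2 | 0.1200 | 0.1800 | 0.816 | 0.067 |

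**Step 2: simulation of the M-estimator itself.** Bisquare weights (c = 4.685), one MAD scale, H1 covariance, 50 vs 25, equal true location; the model has treatment, one binary stratum and baseline. Separate runs used 5,000 to 20,000 replicates per scenario with normal, t3 or t4 errors. Actual level at nominal 0.025:

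| r | level |
|---|---|
| 0.5 | 0.012-0.017 |
| 0.67 | 0.014-0.020 |
| 1 | about 0.03 |
| 1.25 | 0.04-0.05 |
| 1.5 | 0.06-0.08 |
| 2 | 0.11-0.15 |

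For r above 1 the distortion exceeds Step 1, because the single scale also down-weights the more variable placebo arm. At r = 2 with normal errors, the H2 and H3 covariances give about 0.10-0.11 and 0.06-0.07.

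**Step 3: coverage.** With symmetric errors a true shift between arms does not change these rates, so coverage is one minus the level. The nominal 97.5% interval covers about 92-94% at r = 1.5 and 85-89% at r = 2.

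**Step 4: how r could arise.** If the drug lowers values proportionally and nothing else changes, the percent-change SD shrinks by the same factor. A ratio r then needs a fall of 1 − 1/r: 20% for 1.25, 33% for 1.5 and 50% for 2.

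**Step 5: remedies, same settings.** An HC3-type sandwich SE with a t reference gave 0.018-0.033 with normal and t4 errors. A plain sandwich with a normal reference reached about 0.041 at r = 2. Arm-specific M-fits with Satterthwaite degrees of freedom gave 0.025-0.030 for r from 0.5 to 2 with normal and t3 errors. With skewed (lognormal) errors the HC3 version gave 0.041 at r = 1.5 and 0.080 at r = 2. Missing data and imputation were not simulated.

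**The case against.** The strongest objection is that the inflating case is a narrow null. If alirocumab does nothing to Lp(a) or TG, both arms share one distribution and the level is about 0.03. If it lowers them proportionally, the placebo arm does become more variable, but the null is then false and no type I error is possible. Varied response, including Week 12 dose changes confined to alirocumab patients, would widen the alirocumab arm, which is the conservative direction. All of this stands as a limit on the type I error claim. It does not remove the coverage problem, which applies whenever the spreads differ.

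The size also depends on settings that the SAP leaves open. H1 is assumed, the upper end falls under H2 or H3, and the method paper that the SAP cites is not available here. Symmetric errors are also a simplification for endpoints chosen for non-normality. With skew and unequal spread, the M-estimate targets a different location in each arm, so the level can exceed the range shown.

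A reader might infer that the sponsor has accepted unequal variances for these endpoints and overlooked them. The documents do not support that. Table 3 says only that the change followed regulatory feedback, the feedback is not included, and the omission could be deliberate. Finally, these tests are reached only after the primary and the first 11 key secondary tests have succeeded.

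**Conclusion.** The point holds as a SHOULD-level improvement. In each cohort, four alpha-controlled tests rely on an equal-spread assumption that SAP v2 dropped in the MMRM and the listed ANCOVAs, and the SAP gives no reason for keeping it here. The consequence is conditional: near-nominal at equal spread, a level of about 0.04-0.05 at a ratio of 1.25 and 0.06-0.08 at 1.5, and mild conservatism when alirocumab is the more variable arm. These figures rest on an assumed SD ratio, an assumed H1 covariance, symmetric errors and complete data.

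A reader might infer that the trial's error control has failed, or that these tests really run at 0.14. Neither follows. Levels of 0.11-0.15 require placebo to be twice as variable with no difference in location, and no figure in the documents suggests that. The primary endpoint and the first 11 key secondary tests do not use this method.

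**What to change.** In SAP 2.4.4.2.2, keep the M-estimate and the percent-change endpoint. In each imputed data set, replace the default standard error with one of:
- a small-sample heteroscedasticity-consistent (HC3-type) sandwich SE; or
- arm-specific M-fits with Satterthwaite degrees of freedom.

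Combine by Rubin's rules with a t reference and complete-data degrees of freedom. For the single-model sandwich in the Q4W cohort at planned size, that is 75 − 4 = 71 (intercept, treatment, weight stratum, baseline). State the chosen covariance explicitly. Apply the change to both cohorts and to the on-treatment versions, and settle it before the first-step analysis.

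The cost is SAP wording and a short macro, with no new data and no departure from the M-estimation named in the protocol. Intervals may become slightly wider or narrower. The repair is only partial when errors are strongly skewed and spreads differ. For that case, an unequal-variance ANCOVA on the log ratio to baseline can be added, but only as a sensitivity analysis, because it changes the listed endpoint.

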2.4.4.2.3 Binary endpoints

Binary secondary efficacy endpoints defined in in Section 2.1.3.2 (ie, proportion of patients achieving at least 30% reduction, 50% reduction in LDL-C at Week 12 or Week 24) will be analyzed using multiple imputation approach for handling of missing values as described for non-normally distributed endpoints but without log-transformation (see Section 2.4.4.2.2 for details about multiple imputation).

For each simulation leading to negative imputed value, another value will be redrawn using MINIMUM option of MI SAS procedure.

For the Q2W dosing regimen cohort, the binary endpoint at time point of interest will be derived from observed and imputed lipid values at this time point. Multiple imputation will be followed by stratified logistic regression with treatment group (alirocumab, placebo) as main effect and corresponding baseline value(s) as covariate, stratified by randomization factors (as per IVRS, previous participation [yes or no] to DFI14223 study, baseline body weight [<50 or \geq 50 kg]) Combined estimates of odds ratio 97.5% CIs, and p-value will be obtained through the SAS MIANALYZE procedure, for the alirocumab group versus the placebo group.

For the Q4W dosing regimen cohort, the same strategy will be conducted using a stratified logistic regression with treatment group (alirocumab, placebo) as main effect and corresponding baseline value(s) as covariate, stratified by randomization factors (as per IVRS, baseline body weight [<50 or \geq 50 kg]).

In the data dependent case such logistic regression is not applicable (eg, the response rate is zero in one treatment arm and thus the maximum likelihood estimate may not exist), a stratified exact conditional logistic regression would be performed to compare treatment effects. LDL-C values missing during the on-treatment period will be imputed using the last observation carried forward (LOCF) approach, as well as post-treatment missing values for patients who discontinued due to the COVID-19 pandemic. The LOCF imputation method will consist of using the last value obtained up to the Week 24 analysis window (Week 12 respectively) to impute the missing Week 24 value (Week 12 respectively). Other post-treatment missing values will be considered as failure.

In case of computing issues with exact logistic regression, the baseline level(s) will be entered in the model as a categorical variable(s) using quartiles. In case the model would not converge with stratification variables, an unstratified exact logistic regression will be performed. Exact odds ratio versus placebo, 97.5% CIs, and p-value will be provided.

Binary secondary efficacy endpoints analyzed with the on-treatment estimand will be analyzed using the same imputation model, but only including on-treatment values (see Section 2.4.4.2.1) in this model in the mITT population.

